6.2.2 Race

Where more than one race category has been selected for a subject, these race categories will be combined into a single category labeled “Multiple Race” in the summary tables. The listings will reflect the original selected categories.

6.2.3 Age

Age at informed consent will be calculated in SAS as

Age (years) = floor ((intck('month',BRTHDTC,RFICDTC) - (day(RFICDTC) < day(BRTHDTC))) / 12)

where BRTHDTC is reported birthdate and RFICDTC is informed consent date.

6.2.4 Baseline

Baseline is defined as the last non-missing value (either scheduled, unscheduled or repeat) before the subject receives the first dose of study drug.

For variables that will be summarized by treatment, the Baseline for each period is defined as the last non-missing value (either scheduled, unscheduled or repeat) that is collected before dosing, in the respective period.

Change from Baseline = Result at visit / timepoint – Result at Baseline

6.2.5 Duration / Study Day / Time

Study day will be calculated as the number of days from first dose of study drug.

- date of event – date of first dose of study drug + 1, for events on or after first dose
- date of event – date of first dose of study drug, for events before first dose

6.2.6 Conventions for Missing and Partial Dates

It is not expected that there will be any missing dates, however in the rare case that an Adverse Event (AE) start date or time is missing and it is unclear whether the AE is treatment emergent or not then a conservative approach will be taken and it will be assumed that the AE occurred after first dosing.

Similarly, if Concomitant medications have missing end date and it is unclear whether it is prior or concomitant, then a conservative approach will be taken, and it will be assumed that the medication was concomitant.

QMD Ref: Worldwide-TMP-ST-006-4.0 Effective: 12Aug2019	Governing QMD: Worldwide-SOP-ST-001
Confidentiality Statement	
This document is the property of Worldwide Clinical Trials Inc. and may not be duplicated, copied, altered or removed from company without prior approval from Worldwide Quality Assurance or in compliance with Worldwide Standard Operating Procedures.	

Worldwide Clinical Trials Controlled Quality Management Document		
 WORLDWIDE CLINICAL TRIALS	Sponsor: Protocol Number:	Opiant Pharmaceuticals OPNT003-PK-002

All dates presented in the individual subject listings will be as recorded on the Electronic Case Report Form (eCRF).

6.2.7 Inexact Values

In the case where a safety laboratory variable is recorded as “> x”, “ \geq x”, “ $<$ x” or “ \leq x”, a value of x will be taken for analysis purposes.

6.2.8 Not Done / Missing

For safety assessments where shift summaries are required (such as, physical examination), records will be imputed for all subjects who received study drug in the respective part in all scheduled visits and marked as ‘Not Done/Missing’ if either the subjects did not attend the visit, or discontinued or had missing assessment at the respective visit.

6.2.9 Unscheduled Visits

Only scheduled post-baseline laboratory and vital signs values will be tabulated. Post-baseline repeat / unscheduled assessments will be disregarded, although these post-baseline assessments will be listed in the relevant appendices to the CSR.

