	
minutes) post-dose. ECG assessment will be conducted within \pm 5 minutes of the nominal blood collection at 20 minutes, and \pm 15 minutes of the nominal blood collections at 1 and 6 hours post-dose.
 
Vital signs will be measured pre-dose and at approximately 15 and 30 minutes, and \pm 15 minutes of the nominal blood collections at 1, 2, 4 and 8 hours post-dose. Vital signs will also be measured if the subject displays any change in condition including lightheadedness, dizziness, syncope, nausea, vomiting or tachy/bradyarrhythmia as noted on continuous cardiac monitoring.
 
Nasal passage examination will be conducted in both nostrils pre-dose, at approximately 5 minutes and \pm 15 minutes of the nominal blood collections at 1 and 8 hours post-dose.
 
Smell test will be conducted pre-dose and \pm 15 minutes of the nominal blood collections at 1 and 4 hours post-dose.
 
Tolerability assessed via AE query and concomitant medications will be reviewed.
 
On the day after dosing (day 2,8 and 14) tolerability via AE query will be assessed, concomitant medications reviewed, vital signs measured, the smell test will be conducted and examination of the nasal passage performed in both nostrils at approximately 24 hours post-dose.
 
On the second day after dosing (day 3 and day 9) tolerability via AE query will be assessed, concomitant medications reviewed, vital signs measured and examination of the nasal passage performed in both nostrils at approximately 48 hours post-dose.
 
On days 4, 5, 10 and 11 tolerability will be assessed, and concomitant medications reviewed. On the days before the next dosing (days 6 and 12) tolerability will be assessed, concomitant medications reviewed, a urine pregnancy test (females only) and 12-lead ECG performed. On the day of clinic discharge (day 15) from the inpatient stay the following procedures will be performed: assess tolerability via AE query, update on concomitant medications, vital signs at approximately 48 hours post-dose, physical examination, weight, examination of the nasal passage in both nostrils at approximately 48 hours post-dose, smell test,,

--	--

	12-lead ECG, serum pregnancy test (females only), clinical chemistry, coagulation markers, hematology and urinalysis. AEs will be assessed by spontaneous reports by subjects, by examination of the nasal mucosa and by measuring vital signs, ECG and clinical laboratory parameters.
Planned Sample Size:	Twenty-four subjects

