6.11.3 Vital Signs

All Vital signs except temperature will be tabulated for Baseline, 0.25 h, 0.5 h, 1 h, 2 h, 4 h, 8 h, 24 h and 48 h post-dose and the respective changes from Baseline, per treatment. Temperature will be tabulated for Baseline and EOS/ET and the change from Baseline, per treatment. In addition, vital signs values will be tabulated for Baseline, EOS/ET, and change from Baseline to EOS/ET by treatment sequence and overall.

Descriptive statistics for the following vital signs will be presented:

QMD Ref: Worldwide-TMP-ST-006-4.0 Effective: 12Aug2019	Governing QMD: Worldwide-SOP-ST-001
Confidentiality Statement	

This document is the property of Worldwide Clinical Trials Inc. and may not be duplicated, copied, altered or removed from company without prior approval from Worldwide Quality Assurance or in compliance with Worldwide Standard Operating Procedures.

Worldwide Clinical Trials Controlled Quality Management Document		
 WORLDWIDE CLINICAL TRIALS	Sponsor:	Opiant Pharmaceuticals

- Systolic blood pressure (mmHg)
- Diastolic blood pressure (mmHg)
- Pulse rate (beats/min)
- Respiration rate (breath/min)
- Body temperature (°Celsius)

Also, Shift tables in relation to investigator assessment i.e. Normal, Abnormal NCS (Not Clinically Significant), and Abnormal CS (Clinically Significant), from Baseline to each post-baseline visits will be presented. EOS/ET visit will be presented by Treatment sequence and all other post-baseline visits will be presented by treatment.

All vital sign data, including details of any clinically significant values will be listed.

In Mock Shells: Tables 14.3.5.1 and 14.3.5.2, Listing 16.2.8.10

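### Vital signs taken because a subject has become symptomatic enter no vital-sign table and reach the report only as listing entries

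*SAP*

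**What the plan says.** The protocol synopsis (Study Design) sets fixed post-dose times for vital signs and then adds a symptom trigger: "Vital signs will also be measured if the subject displays any change in condition including lightheadedness, dizziness, syncope, nausea, vomiting or tachy/bradyarrhythmia".

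SAP 6.2.9 states which readings reach the tables: "Only scheduled post-baseline laboratory and vital signs values will be tabulated". It continues: "Post-baseline repeat / unscheduled assessments will be disregarded, although these post-baseline assessments will be listed", the listing being in the CSR appendices.

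SAP 6.11.3 plans two displays. The descriptive table runs on nominal times: "All Vital signs except temperature will be tabulated for Baseline, 0.25 h, 0.5 h, 1 h, 2 h, 4 h, 8 h", followed by 24 h and 48 h. The shift table uses the investigator's three categories, Normal, Abnormal NCS and "Abnormal CS (Clinically Significant), from Baseline to each post-baseline visits will be presented". The same section promises a full listing of vital-sign data with details of clinically significant values (Listing 16.2.8.10).

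The post-database-lock addendum keeps the same two tables, 14.3.5.1 and 14.3.5.2, and does not touch 6.2.9.

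**The concern.** Leaving unscheduled readings out of by-timepoint means is ordinary practice, because such readings have no timepoint to belong to. A shift table has a different purpose. It tells the reader whether subjects moved from normal to clinically significant abnormality. Here the protocol orders extra readings specifically because a subject is unwell, and the SAP then excludes those readings from the table meant to show abnormality.

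Safety and tolerability is the secondary objective (SAP section 2), and vital signs are a named safety endpoint (SAP 3.2). The by-treatment vital-sign tables could show no shift to clinically significant while the listing contains one. The reader would have to find it and tally it by hand.

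**Working it through.** The plan gives no figure on this point, so the check sets the passages side by side.

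1. **Status of a triggered reading.** The protocol requires it at any change in condition and gives it no nominal time. The SAP does not define unscheduled and does not mention triggered readings. With no nominal time, a triggered reading can only be unscheduled in the sense of 6.2.9.

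2. **Descriptive table.** Its rows are Baseline and 0.25, 0.5, 1, 2, 4, 8, 24 and 48 h. None can hold a triggered reading.

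3. **Shift table.** One could argue that the first sentence of 6.2.9 concerns numerical values, whereas the shift uses investigator categories. The result is the same, because the second sentence disregards the assessments themselves, and 6.11.3 defines the shift per visit with no worst-value or event-triggered row.

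4. **Other routes into the report.** The reading is in Listing 16.2.8.10. The triggering symptom may be counted as a TEAE, assigned to the treatment received immediately before onset (SAP 6.11.1). Those tables give term, severity and relationship. They do not give the vital-sign value or its clinical-significance category.

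5. **Treatment of Baseline.** SAP 6.2.4 lets an unscheduled or repeat reading serve as Baseline. The exclusion therefore applies only after dosing.

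6. **What a worst-value summary would do.** Order the categories Normal < Abnormal NCS < Abnormal CS. For one subject in one period, scheduled readings are a subset of all readings, so worst(all) ≥ worst(scheduled). A worst-value shift that includes unscheduled readings can only hold or raise the number of clinically significant subjects, compared with a worst-value shift on scheduled readings alone.

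7. **Would a scheduled reading usually coincide with the event?** This is an illustration only.
   - Telemetry runs to about 6 h post-dose, which is 360 min. The scheduled windows at 1, 2 and 4 h are ±15 min, so they cover 3 × 30 = 90 min, and 90/360 = 25%.
   - The 15 and 30 min readings have no stated window. Assuming ±5 min adds 2 × 10 = 20 min, and 110/360 = 31%.
   - Over 48 h (2,880 min), four windows of 30 min (1, 2, 4, 8 h), one of 60 min (24 h) and half of one (48 h) give 120 + 60 + 30 = 210 min, and 210/2,880 = 7.3%. With the extra 20 min it is 230/2,880 = 8.0%.
   - If event times were uniform, which is an assumption, 69% to 75% of events in the telemetry period would fall outside every scheduled window.

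**The case against.** The strongest reply is that nothing is lost from the report. The readings are listed with their clinical-significance details, and the symptoms that trigger them can be reported as adverse events and tabulated by treatment, severity and relationship. The vital-sign analysis is descriptive, with no test or decision rule attached. A per-visit shift table has no natural cell for a reading without a nominal time. The available protocol text prescribes no analysis of triggered readings, so the SAP contradicts nothing. All of this stands, and it keeps the point at low priority.

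Several stronger readings are tempting but not supported:

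- **That the rule removes the most abnormal values.** It excludes by timing, not by abnormality. Nothing in the documents shows that a reading taken for nausea or lightheadedness is more extreme than a scheduled one.
- **That the current tables lean one way, toward normal.** The rule also drops repeats. Where a repeat re-checks an abnormal scheduled value, the abnormal value stays and a possibly normal repeat is dropped. The net direction for per-visit results is unknown.
- **That the comparison of 3 mg with 6 mg is biased.** A difference between regimens in triggered readings is possible, but no passage indicates one.
- **That each affected subject moves a reported incidence from 1/24 = 4.2% to 0%.** The per-visit shift table reports no overall incidence of clinically significant abnormality, so no such figure exists to be moved.

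A worst-value summary also has weaknesses. Subjects with more readings have more chances of an abnormal one. Posture may be mixed as well: the schedule footnotes specify supine at 15 and 30 min and sitting at the other post-dose times, and state none for triggered readings. These call for a footnote. They do not justify leaving the readings out of every table.

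**Conclusion.** The point holds as a gap in the safety display. Under SAP 6.2.9 and 6.11.3, symptom-triggered vital signs enter neither the descriptive table nor the shift table. A subject whose only clinically significant reading was triggered would not be shown as such in any by-treatment vital-sign table.

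This rests on one reading of the text, that a triggered measurement counts as unscheduled, and the fixed timepoints in 6.11.3 leave no other place for it. The number of affected subjects and any difference between regimens cannot be sized from the documents. The window coverage in the working depends on assumed uniform event times and does not estimate that number. PK results and the sample size are unaffected. The change is worth making because it is cheap, but no conclusion of the study depends on it.

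**What to change.** Keep the by-timepoint statistics and per-visit shifts on scheduled readings, and limit the exclusion in 6.2.9 to those summaries. Add one block to Table 14.3.5.2: by treatment, the shift from period Baseline to the worst post-dose investigator assessment in the period, over scheduled, repeat and unscheduled readings. Footnote that triggered readings have no fixed time or stated posture and that the number of readings differs between subjects.

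The derivation rule should also say how Day 15 is handled. SAP 6.2.1 maps it to EOS/ET with no analysis period, although the third period's 48 h reading is taken that day.

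Because the database is locked, report this as an additional analysis, justified in the CSR as SAP sections 6 and 7 provide. The cost is a short derivation rule, one row block and a further post-lock change. Counts of clinically significant abnormality may look slightly less favourable. The data are already collected.

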6.2.10 PK Parameters

6.2.10.1 Concentration-Time Data

Blood samples for the characterization of nalmefene in plasma will be collected prior to dosing (within 15 minutes) and at approximately 2.5, 5, 7.5, 10, 15, 20, 30, 45 minutes and 1, 2, 3, 4, 6, 8, 12, 18, 24 and 48 hours after drug administration for each study period.

Treatments to be administered are:

- Treatment A: T1: 3 mg, one 0.1 mL spray in one nostril.
- Treatment B: T2: 6 mg, one 0.1 mL spray in each nostril.
- Treatment C: T3: 6 mg, two 0.1 mL sprays in one nostril.

Individual plasma concentrations of nalmefene will be listed by treatment and summarized by descriptive statistics: number of non-missing observations (n), arithmetic mean (mean), standard deviation (SD), median, minimum (min), maximum (max), and coefficient of variation (CV%). Individual and mean plasma concentrations versus time profiles will be presented graphically in linear and semi-logarithmic scale. For individual subject concentration-time data, spaghetti plots (all subjects in one plot per treatment) and individual subject plots (all three treatments in one plot

QMD Ref: Worldwide-TMP-ST-006-4.0 Effective: 12Aug2019	Governing QMD: Worldwide-SOP-ST-001
Confidentiality Statement	

This document is the property of Worldwide Clinical Trials Inc. and may not be duplicated, copied, altered or removed from company without prior approval from Worldwide Quality Assurance or in compliance with Worldwide Standard Operating Procedures.

Worldwide Clinical Trials Controlled Quality Management Document		
 WORLDWIDE CLINICAL TRIALS	Sponsor:	Opiant Pharmaceuticals

for each subject) will be created. Mean data will be plotted using nominal sample times and individual data will be plotted using actual times.

For the presentation of concentration-time data, concentrations that are below the limit of quantitation (BLQ) will be set to zero.

6.2.10.2 PK Parameters

Concentration-time data for nalmefene will be analyzed using noncompartmental methods in Phoenix™ WinNonlin® (Version 8.1 or higher, Certara, L.P.) in conjunction with the internet-accessible implementation of Pharsight® Knowledgebase Server™ (PKSO; Version 4.0.4, Certara, L.P.).

During the PK analysis, concentrations below the limit of quantitation (BLQ) up to the time of the first quantifiable concentration will be treated as zero. Embedded (values between 2 quantifiable concentrations) and terminal BLQ concentrations will be treated as “missing”.

Calculation of the PK characteristics will be based on actual elapsed times [h] (relative to time of dose). If actual times are missing, nominal times may be used following discussion with Sponsor and will be documented in the CSR.

The following PK parameters will be calculated for nalmefene:

Parameter	Definition
C_{max}	Maximum concentration, determined directly from individual concentration-time data
$C_{max}/Dose$	C_{max} adjusted for the nominal administered dose
T_{max}	Time of maximum observed concentration, obtained directly from the observed concentration versus time data
AUC_{0-x}	The area under the concentration-time curve from time 0 (predose) to time x, where x = 2.5, 5, 7.5, 10, 15, 20, and 30 min; calculated by the linear-up/log-down trapezoidal method
$AUC_{0-x}/Dose$	AUC_{0-x} adjusted for the nominal administered dose
AUC_{0-t}	Area under the concentration-time curve from time-zero to the time of the last quantifiable concentration; calculated using the linear-up/log-down trapezoidal method

QMD Ref: Worldwide-TMP-ST-006-4.0 Effective: 12Aug2019	Governing QMD: Worldwide-SOP-ST-001
Confidentiality Statement	

This document is the property of Worldwide Clinical Trials Inc. and may not be duplicated, copied, altered or removed from company without prior approval from Worldwide Quality Assurance or in compliance with Worldwide Standard Operating Procedures.

Worldwide Clinical Trials Controlled Quality Management Document			
 WORLDWIDE CLINICAL TRIALS	Sponsor:	Opiant Pharmaceuticals	
	Protocol Number:	OPNT003-PK-002	

Parameter	Definition
AUC _{0-t} /Dose	AUC _{0-t} adjusted for the nominal administered dose
AUC _{inf}	Area under the concentration–time curve extrapolated to infinity, calculated as: $AUC_{inf} = AUC_{0-t} + C_{last}/\lambda_z,$ where C_{last} is the last quantifiable concentration and λ_z is the terminal elimination rate constant. The percentage of AUC _{inf} based on extrapolation should be <30.0%
AUC _{inf} /Dose	AUC _{inf} adjusted for the nominal administered dose
AUC%Extrap (%)	The percentage of AUC _{inf} based on extrapolation, calculated as: $(AUC_{inf} - AUC_{0-t})/AUC_{inf}] \times 100$
K _{el} (λ_z ; Lambda-z)	Lambda-z (K _{el} , λ_z) is the terminal-phase elimination rate constant, estimated by linear regression of logarithmically-transformed concentration versus time data (linear-up/log-down trapezoidal method; additional criteria are summarized below)
t _{1/2}	The terminal phase half-life for drug concentrations in plasma is calculated as: $t_{1/2} = \ln(2)/\lambda_z$
CL/F	The apparent total plasma clearance, calculated as: $CL/F = Dose/AUC_{inf}$, where F is the bioavailability
V _z /F	The apparent volume of distribution, calculated as: $V_z/F = Dose/(AUC_{inf} \times \lambda_z)$, where F is the bioavailability
C _{last}	Last quantifiable concentration
T _{last}	Time of the last quantifiable concentration

Lambda-z (K_{el}) Criteria

The following criteria will be used to report K_{el}:

- At least three quantifiable concentrations will be used in the regression

QMD Ref: Worldwide-TMP-ST-006-4.0 Effective: 12Aug2019	Governing QMD: Worldwide-SOP-ST-001
Confidentiality Statement	

This document is the property of Worldwide Clinical Trials Inc. and may not be duplicated, copied, altered or removed from company without prior approval from Worldwide Quality Assurance or in compliance with Worldwide Standard Operating Procedures.

Worldwide Clinical Trials Controlled Quality Management Document		
 WORLDWIDE CLINICAL TRIALS	Sponsor: Protocol Number:	Opiant Pharmaceuticals OPNT003-PK-002

- C_{max} or data prior to C_{max} will not be included in the regression.
- The adjusted regression coefficient (R^2 adj) should be ≥ 0.80 .

If these acceptance criteria are not met, K_{el} and descriptive parameters (K_{el} time range, Adj R^2 , etc.) will be retained in a parameter listing for informational purposes; K_{el} will be excluded from summary statistics. Parameters calculated using K_{el} ($t_{1/2}$, CL/F, V_z/F) will be reported as ND (not determinable).

If K_{el} acceptance criteria are met and AUC_{inf} is estimable, the following criteria are used to report AUC_{inf} :

- The percentage of AUC_{inf} based on extrapolation should be $<30.0\%$.

If the percentage of AUC_{inf} based on extrapolation is 30.0% or greater, AUC_{inf} and $AUC_{\%extrap}$ will be excluded from summary statistics, subsequent PK calculations (e.g. CL/F, V_z/F), and statistical analysis (e.g. ANOVA).

Individual PK parameters will be listed by treatment and summarized by descriptive statistics: n, mean, SD, median, min, max, CV%, geometric mean, and geometric CV%.

6.3 Conventions

All clinical data listings, summaries, figures and statistical analyses will be generated using SAS (Version 9.4 or higher)¹.

Summaries of the clinical data will be presented by treatment and/or treatment sequence unless otherwise stated.

PK data listings, summaries, figures, and statistical analyses will be generated using Phoenix™ WinNonlin® (Version 8.1 or higher)² or SAS (Version 9.4 or higher)¹. PK concentration data will be summarized by treatment at each nominal sample time. PK parameter data will be summarized by treatment.

Treatment labels will be displayed as follows:

Treatment A

Treatment B

Treatment C

Footnotes describing each treatment will be provided in each output.

Treatment sequence labels will be displayed as follows:

Sequence 1

Sequence 2

Sequence 3

Sequence 4

Sequence 5

Sequence 6

QMD Ref: Worldwide-TMP-ST-006-4.0 Effective: 12Aug2019	Governing QMD: Worldwide-SOP-ST-001
Confidentiality Statement	

This document is the property of Worldwide Clinical Trials Inc. and may not be duplicated, copied, altered or removed from company without prior approval from Worldwide Quality Assurance or in compliance with Worldwide Standard Operating Procedures.

Worldwide Clinical Trials Controlled Quality Management Document		
 WORLDWIDE CLINICAL TRIALS	Sponsor: Protocol Number:	Opiant Pharmaceuticals OPNT003-PK-002

For safety assessment that are summarized by visit/timepoint, treatment and/or treatment sequence will be displayed in footnote as follows:

Treatment A: 3 mg (one 0.1 mL spray of 30 mg/mL nalmefene hydrochloride in one nostril)

Treatment B: 6 mg (one 0.1 mL sprays of 30 mg/mL nalmefene hydrochloride in each nostril)

Treatment C: 6 mg (two 0.1 mL sprays of 30 mg/mL nalmefene hydrochloride in one nostril)

“Sequence 1” represents subjects taking Treatment A in period 1, Treatment B in period 2 and Treatment C in period 3; “Sequence 2” represents subjects taking Treatment B in period 1, Treatment C in period 2 and Treatment A in period 3; “Sequence 3” represents subjects taking Treatment C in period 1, Treatment A in period 2 and Treatment B in period 3; “Sequence 4” represents subjects taking Treatment A in period 1, Treatment C in period 2 and Treatment B in period 3; “Sequence 5” represents subjects taking Treatment B in period 1, Treatment A in period 2 and Treatment C in period 3; “Sequence 6” represents subjects taking Treatment C in period 1, Treatment A in period 2 and Treatment B in period 3.

Listings will be sorted in the following order treatment sequence, subject, visit and parameter unless otherwise stated. All data will be listed.

For clinical data, continuous variables will be summarized by the number of non-missing observations, arithmetic mean, median, standard deviation, and minimum and maximum.

Categorical variables will be summarized by presenting the frequency and percent. Percentages will be based on the number of non-missing observations or the subject population unless otherwise specified. For each variable, all categories will be shown. Zero frequencies (but not the percent) within a category will be presented.

